#### 6.4 Selection of doses

The Jupiter study, using a rosuvastatin dose of 20 mg daily, demonstrated reductions in LDL cholesterol by 50% and hsCRP by 37%; resulting in a 50% reduction in vascular events. The METEOR study reported a significant reduction in cIMT progression after 12 months of rosuvastatin therapy with the divergence continuing to increase with further follow-up out to 24 months. Most rosuvastatin (90%) is excreted unchanged, while 10% undergoes limited metabolism by cytochrome P450 2C9. Pharmacokinetic studies of drug-drug interactions in healthy volunteers have shown that protease inhibitors (PI) in current use caused a 2.4-4.7 fold increase in Cmax and 1.5-3 fold increase in AUC for rosuvastatin. For the participants receiving a non-PI based cART regimen, a dose of 20 mg rosuvastatin (1 x20 mg tablet) will be used. Participants on any PI-based cART regimen will receive 1 X 10 mg rosuvastatin (effective exposure 20 mg daily).

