#### 6.6 Sample size

The METEOR study of rosuvastatin in HIV negative participants with low to intermediate CVD risk found a mean Common Carotid Artery cIMT progression rate of 0.0088 mm/2 years in the placebo arm and 0.0004mm/2 years in the rosuvastatin arm^22, giving an effect size of 0.0084 mm/2 years (95% relative reduction) with a standard deviation (SD) of 0.033 mm/year. A pilot study in HIV positive patients at the AH (n=10) found that in participants treated with non-nucleoside reverse transcriptase inhibitors (the most common cART regimen), the mean cIMT progression rate was 0.04 mm/year with a SD of 0.0782 mm (personal communication [name], Baker IDI), similar to estimated values proposed for cIMT progression in HIV positive participants at low to intermediate CVD risk (mean 0.045 mm/year, SD 0.08 mm; 62).

Conservatively assuming a cIMT progression rate of 0.080 mm with a SD of 0.09 mm over 2 years and near stabilisation of cIMT (95% relative reduction) with rosuvastatin, we can assume an effect size of 0.076 mm with a SD of 0.09 mm. Sample size was calculated using an independent groups t-test with an alpha threshold of 1% and a power of 90%. Based on these hypotheses, with 44 participants in each group this study will be able to detect an effect

size of 0.076 mm with a SD of 0.09 mm over 2 years between the 2 groups. With an estimated 15% total drop-out rate over 96 weeks, we estimate that a total study population of 102 will be required.

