### 9.4 Removal of participants from therapy/assessment

Participants will be withdrawn from the trial if:

1. A SAE occurs which is thought to be related to involvement in the study
2. The subject withdraws consent
3. The subject becomes pregnant
4. The subject is diagnosed with clinical cardiovascular disease
  - a. Cardiovascular
    - i. Acute myocardial infarction (AMI)
    - ii. Development of angina
    - iii. New ECG changes consistent with cardiovascular disease
  - b. Cerebrovascular
    - i. Stroke or Transient Ischaemic Attack (TIA)
  - c. Peripheral vascular disease
    - i. Symptomatic claudication
5. The subject is diagnosed with an acute serious medical illness that would be a contraindication to statin therapy i.e.
  - a. Acute viral hepatitis ( A, B or C)
6. CK or transaminase elevation (> 3 times)

7. Subject is judged by the investigator to be at significant risk of failing to comply with the provisions of the protocol so as to cause harm to self or seriously interfere with the validity of the study result.

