### 1. Analysis of the primary endpoint:

To study rosuvastatin effect from baseline to week 96 on mean and / or of left and right maximal IMT progression, multi-levels, repeated measures, linear mixed-effects models adjusted for demographics and/or traditional CVD risk factors and centre (Melbourne, Geneva, Lausanne, Berne, Zurich, Basel, St. Gallen, Lugano) will be used. Levels used for the data will be patient and carotid artery locations (CCA, ICA, BIF and ECA) within patients; the repeated measure will be time (baseline, week 48 and week 96).

A comparison across arms (placebo/rosuvastatin) of missing IMT measurements (0, 1, 2 or 3 missing per IMT location) will be performed using a Chi-Square Test with a threshold of 1%.

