### 2. Analysis of the secondary endpoints:

To study rosuvastatin effect from baseline to week 48 on mean and / or of left and right maximal IMT progression, multi-levels, repeated measures, linear mixed-effects models adjusted for demographics and/or traditional CVD risk factors and centre will be used. Levels used for the data will be patient and carotid artery locations (CCA, ICA, BIF and ECA) within patients; the repeated measure will be time (baseline and week 48).

Repeated measures linear mixed-effects models adjusted for demographics and/or traditional CVD risk factors and centre will be used to assess the association between the arms (placebo/rosuvastatin) and each of the following parameters at week 0, 12, 24, 48, 72 and 96. We will test the interaction term between the arms and time (Month 0, 6, 12 and 24) to determine whether the rate of progression of the following parameters differed between arms (rosuvastatin versus placebo): Fasting Total Cholesterol, low-density lipoprotein (LDL)-cholesterol, high-density lipoprotein (HDL)-cholesterol, triglycerides and glucose.

Biomarkers of inflammatory process (sCD14, sCD163, neopterin, S-VCAM-1, adiponectin, CCL2, inflammatory (CD16+) monocyte expression of CD38, CX3CR1 and CD11b) will be

analysed using the same kind of regression with the same adjustments as described above including (LDL)-cholesterol and (HDL)-cholesterol.

The rate of adverse effects (symptomatic and biochemical) from the safety report will be summarized using frequency and percentage.

All efficacy analyses will compare the randomised treatment groups on an intention to treat basis regardless of treatments received during the study, including all patients with data at randomisation and at least one follow-up visit. Primary endpoint analyses will use a last value-carried forward approach for any patients permanently lost to follow-up. Secondary endpoints analyses will only include available data.

Statistical analysis will be performed using STATA Release 12.0 or updated version (Stata Statistical Software: Release 12.0, Stata Corporation, and College Station, USA).

We plan to recruit 102 patients. Drop outs will not be replaced unless the number surpasses the attrition rate of 15%.

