An interim analysis will be performed at 48 weeks. The final analysis at 96 weeks will be conducted when all patients will have completed the follow-up visits or have been permanently lost to follow-up, and the study database is signed off as checked and complete.

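### Carrying the last cIMT value forward freezes a progressing primary endpoint: at equal 15% loss the planned effect shrinks by 0–15%, and unequal loss in either direction can raise type I error

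*Combined protocol and SAP*

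**What the plan says.** The rule stands in section 17 under item 2 (secondary endpoints) but governs the primary one: "Primary endpoint analyses will use a last value-carried forward approach for any patients permanently lost to follow-up". The same paragraph defines the intention-to-treat set as "including all patients with data at randomisation and at least one follow-up visit". No sensitivity analysis accompanies the rule.

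Item 1 of section 17 specifies a multi-level linear mixed model in which "the repeated measure will be time (baseline, week 48 and week 96"). It adds a chi-square comparison of missing IMT measurements by arm at the 1% level, with no stated consequence. Section 17 closes by timing the final analysis for "when all patients will have completed the follow-up visits or have been permanently lost to follow-up".

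The flow chart (section 5) and sections 12.8 and 12.10 place cIMT scans at screening, week 48 and week 96 only. The withdrawal visit (the second section numbered 12.1) neither requires nor excludes a scan.

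On the expected course, section 6.4 describes the cited rosuvastatin trial as showing a cIMT benefit at 12 months, "with the divergence continuing to increase with further follow-up out to 24 months". Section 6.6 plans by "Conservatively assuming a cIMT progression rate of 0.080 mm with a SD of 0.09 mm over 2 years", a 95% reduction on rosuvastatin, and "With an estimated 15% total drop-out rate over 96 weeks".

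Withdrawal triggers in section 9.4 include "CK or transaminase elevation (> 3 times") and newly diagnosed cardiovascular disease. Section 11.3 adds significant plaque.

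**The concern.** Carrying the last value forward assumes that progression stops at dropout. The plan assumes the opposite. A lost participant is scored at the week-48 change or, with no later scan, at a change of zero. The mixed model in item 1 can use incomplete scan series, so the imputation is not needed.

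Two readings are left open, and they alter the result:

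- The follow-up-visit condition may mean any visit, so that week 12 or 24 (no scan) suffices and the screening scan is carried. It may instead mean a visit with a scan, so that only week 48 can be carried.
- Withdrawn participants may or may not count as lost. The timing sentence sorts everyone into completed or lost, which suggests that they do, but nothing says so.

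At equal loss the stake is an attenuated estimate. If the amount or timing of loss differs between arms, the frozen arm appears to progress less. With the screening scan carried, heavier or earlier loss on rosuvastatin creates false benefit, and the same on placebo creates false harm. With a scan required, only losses after week 48 are frozen, so the arm with more late losses sets the direction. The withdrawal triggers include drug-linked and outcome-linked events, so the documents do not show which arm would lose more.

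**Working it through.** **Inputs.** From section 6.6: 2-year progression 0.080 mm on placebo and 0.004 mm on rosuvastatin (95% reduction), SD 0.09 mm, alpha 1%, power 90%, 44 evaluable per group, 15% loss, 102 randomised (51 per arm), and a pilot SD of 0.0782 mm (n = 10), used as the 1-year SD. Assumed: the split of loss by arm and time, and linear progression, so that half the effect is present at week 48.

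**The plan's own figure.** A two-sided t-test with difference 0.076 mm and SD 0.09 mm needs 44 per group (power 90.5%). A one-sided test would need 38, so two-sided is used here. 88 × 1.15 = 101.2, rounded up to 102. 102 × 0.85 = 86.7, about 43 per group (89.7%).

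**Equal 15% loss, drug works.** Effect = 0.076 × [1 − q(1 − f)], where q is the share of analysed participants carried forward and f the share of the effect present at the carried scan.

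| Reading | Shrinkage | Effect (mm) |
|---|---|---|
| All lost after week 48, that scan carried | 0.15 × 0.5 = 7.5% | 0.0703 |
| Half before week 48 (screening scan carried), half after | 0.075 × 1 + 0.075 × 0.5 = 11.25% | 0.0675 |
| All lost before week 48, screening scan carried | 0.15 × 1 = 15% | 0.0646 |
| Scan required, half lost early and excluded | (0.075 / 0.925) × 0.5 = 4.05% | 0.0729 |
| Scan required, all lost early and excluded | 0% | 0.0760 |

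If carry-forward applies to only half the dropouts and the rest are excluded, shrinkage is about 4% (late) to 8% (early). Without linearity, late-loss shrinkage is 0.15 × 0.3 = 4.5% if 70% of the effect is present by week 48, and 0.15 × 0.7 = 10.5% if 30% is.

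**Simulation.** 40,000 trials per scenario; t-test on the filled-in week-96 change. The correlation of week-48 and week-96 change was 0.575. This follows if each year's increment has SD 0.0782: (0.09² / 2) / (0.0782 × 0.09) = 0.575. Covariates and carotid segments were not simulated. Early means all losses before week 48 with the screening scan carried; late means all after week 48. At equal 15% loss, power was 91.3% (late) and 88.6% (early).

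**Unequal loss, no drug effect, both arms progressing 0.080 mm.** Bias = 0.080 × (1 − f) × difference in loss rates.

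| Loss by arm | Bias late / early (mm) | Type I error late / early |
|---|---|---|
| 15% / 15% | 0 / 0 | 1.0% / 0.9% |
| 20% / 10% | 0.004 / 0.008 | 1.2% / 1.9% |
| 25% / 5% | 0.008 / 0.016 | 1.8% / 5.1% |

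The size is the same whichever arm loses more; the direction reverses. With 25% early loss on rosuvastatin, 5.09% of trials falsely showed benefit and 0.01% harm. If a scan is required, 25%/5% gives at most 1.8%. Equal 15% loss, early on one arm and late on the other, gives a bias of 0.15 × 0.040 = 0.006 mm and 1.5% error. With a scan required this case gives 1.3%, and the direction flips. The inflation depends on progression: for 25%/5% it is 1.2–2.0% error at an assumed 0.040 mm, and 1.0–1.1% at 0.0088 mm, the 2-year placebo rate of the cited trial in section 6.6.

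**Unequal loss, drug works.** Placebo 25%, rosuvastatin 5%:

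- Late: 0.080 × 0.875 − 0.004 × 0.975 = 0.0661 mm, power 86.6%.
- Early: 0.080 × 0.75 − 0.004 × 0.95 = 0.0562 mm, power 74.9%.
- Reverse split: 0.0745 mm late, 0.0730 mm early.

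**Mixed model on observed scans** (maximum likelihood on week-48 and week-96 change). Missing at random: 0.076 mm, power 89–91%, type I error 0.9–1.0%. With loss driven by the unseen week-96 change (15% overall, log odds 0.5 to 1.5 per SD), the mixed model gave 0.074–0.065 mm and carry-forward 0.068–0.052 mm. Outcome-linked loss of different strength by arm was not run.

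**The case against.** Item 1 of section 17 already plans a check on unequal missingness. Simplified to a two-by-two test with 51 per arm, it would flag a true 25%/5% split about 63% of the time, so the worst case would usually be noticed. The 5% error also needs several things together: a 20-point gap, every loss before week 48, the screening scan carried, and 0.080 mm progression without a drug effect. No passage supports so large a gap. At 17.5%/12.5% the error is 1.05–1.25%, and at 18.5%/11.5% it is 1.1–1.5%. The attenuation, at most about 0.011 mm, runs toward the null and is below the standard error of 0.09 × √(2/51) = 0.018 mm. The mixed model is itself biased when loss depends on unseen values.

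Much of this stands as a limit on size. The type I argument is secondary to the attenuation. The 15% and 5% bounds also need each early loss to follow a week-12 or week-24 visit, since participants with no follow-up visit are excluded under either reading.

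It does not rescue the rule. The chi-square test has no consequence attached and would flag 20%/10% only about 11% of the time. The bias runs toward the null only when the drug works; with no drug effect, carry-forward can produce benefit or harm. The mixed model was less biased in each outcome-linked case run.

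**Conclusion.** The concern holds and should be fixed. At equal 15% loss the planned 0.076 mm is estimated as 0.070–0.065 mm if all dropouts are carried forward, and anywhere from 0.076 to 0.065 mm across the readings the text permits. Two analysts could therefore report different primary results from the same data. Power and type I error stay near plan in that case. Under unequal loss the error roughly doubles at most for 20%/10% and reaches 5.1% only under the extreme conditions described; it vanishes if cIMT barely progresses.

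The 0% and 15% limits need only that the week-48 difference lies between zero and the week-96 difference. The intermediate figures assume linear progression. Splits by arm and timing are assumptions throughout, and a t-test on change stands in for the full mixed model. Confidence is medium for these reasons.

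**What to change.** Delete the carry-forward sentence and substitute:

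> The primary analysis estimates the rosuvastatin–placebo difference in cIMT change from baseline to week 96 from the mixed model in item 1, fitted by restricted maximum likelihood to every observed cIMT value (baseline, week 48, week 96). Missing cIMT values are not imputed. Scans from withdrawn participants and from those lost are used alike. The analysis set for this endpoint is all randomised participants with a baseline scan; this replaces the follow-up-visit condition.

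The last sentence deliberately changes the analysis set and should be recorded as a change. The choices that item 1 leaves open (mean or maximal IMT, covariates) must be settled for the wording to define one analysis.

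Because outcome-linked withdrawal may break the missing-at-random assumption, add a sensitivity analysis in which dropouts from both arms progress like placebo afterwards. At equal 15% loss it gives 0.076 × 0.925 = 0.0703 mm (late) to 0.076 × 0.85 = 0.0646 mm (early), the same as carry-forward. It keeps that caution, but its expected difference is zero when the drug has no effect, whatever the split, provided loss does not depend on unseen values.

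If carry-forward is kept, keep it only as a further sensitivity analysis, define who counts as lost, and say whether a follow-up visit means a scan. Make the change before the unblinded week-48 efficacy review in section 15.

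The cost is wording and a little analysis, with no extra patients, visits or scans. Mixed-model power of 89–91% matches the plan's 90.5% at 44 per group and 89.7% at about 43.

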## **18 Insurance and Finances**

Insurance for the Melbourne site is set up by AH and applies only to the one site.

Insurance for Swiss sites is set up by the University Hospitals of Geneva (HUG) to cover the damages that may occur within this trial. The insurance applies to all Swiss participating study sites.

*Swiss sites: Costs for the local laboratory tests (haematology, biochemistry, virology) that are not included in the routine HIV patient care will be covered by the patient care payments made to the sites by the leading site, Geneva.*

## **19 Quality Control and quality assurance**

### **19.1 Source documents**

Considered source documents are the patient's medical records including, but not limited to written electronic, magnetic and optical records and scans, x-rays, IMT images and electrocardiograms.

The following data will be considered source data:

- CRF: Compliance assessment, physical examination including measurements, smoking status, self-reported pregnancy or breast-feeding status
- Study medication distribution and return details.

### **19.2 Retention of essential documents**

Essential documents as defined by ICH GCP include the signed protocol and any amendment(s), copies of the completed CRFs, signed Informed Consent Forms from all subjects who consented, hospital records, diary cards and other source documents, IRB/IEC

approvals and all related correspondence including approved documents, drug accountability records, trial correspondence and a list of the subject's names and addresses.

The Investigator must maintain all essential study documentation, and take measures to prevent accidental or premature destruction of these documents. The Investigator must retain the study documentation until at least ten years after completion or discontinuation of the study. After that period of time, the documents may be destroyed according local regulations.

### 19.3 Data protection

Intima carotid ultrasound images will be coded with the subject's ID numbers and transferred for analysis to the cIMT Core Facility, Department of Medicine, **Montreal** Heart Institute, Université de Montréal, **Montreal**, Quebec, Canada **Responsible**: [name]. Transfer of this data will be performed strictly anonymously (without personal identifiers), maintaining confidentiality and in line with both the Australian Privacy Law and the Swiss Federal Law on data protection that correspond to applicable laws of the province of Quebec, Canada.

Plasma samples will be coded with the subject's ID number and stored at the Burnet Institute [name] or at the "sérothèque" (biobank) HUG in Switzerland. Swiss sites will ship the plasma samples to the central biobank ("sérothèque") of the HUG, [name], Geneva University Hospitals, Switzerland.

Samples may need to be transferred from Melbourne to Geneva or vice versa for analysis purposes. Shipment of plasma samples between the AH between AH (Burnet Institute, [name]) and the HUG (Cardiology Laboratory, Hôpitaux Universitaires de Genève, [name]) for storage and testing of inflammatory markers will be performed strictly anonymously and in compliance with the Swiss Federal Law on data protection, which corresponds to applicable privacy laws of Australia and the state of Victoria, Melbourne.

### 19.4 Monitoring, audits and inspections

Independent monitoring of the Swiss sites will be performed to ensure the strict implementation of the protocol and guidelines as well as to check consistency between the source data and the CRF in at least 50 percent of the number of enrolled subjects.

In case of audits or inspections by regulatory authorities or the ethics committee, the investigator will provide direct access to the original data, study documents and the sites facilities as well as to the site's personnel involved directly or indirectly in the trial.

## 20 Publications and presentations

The final data will be presented at one or more scientific meetings. No patient data will be presented that could permit identification of any individual study participant. Publication of data derived from this protocol will be supervised by the Principal Investigator in Melbourne and Geneva in conjunction with all study investigators. No other publication will be made before the primary manuscript has been agreed upon and accepted for publication and without prior approval of the principal investigator in Melbourne.

## 22 Appendix

### 22.1 Case Record Forms

#### 22.1.1 Screening Visit

Screening Visit – Rosuvastatin Trial		
Screening Number		
Date	____/____/____	
Informed Consent Signed	 Yes  No	
Age (years – round number)		
Gender	 Male  Female	
Ethnicity	 Caucasian	
	 Asian	
	 African	
	 Aboriginal/Torres Strait Islander	
Date first diagnosed with HIV	____/____/____	
Prior AIDS defining illnesses	 Yes  No	
List any previous AIDS defining illness	1.	
	2.	
	3.	
	4.	
	5.	
	6.	
	7.	
Currently taking antiretrovirals	 Yes  No	
Change in antiretroviral in last six (6)	 Yes  No	
Total cumulative years on Indinavir		
Total cumulative years on lopinavir		
HIV Viral load been <200 copies/ml for	 Yes  No	
CD4+ T-cell Nadir		
List all past medical history  (Tick box if currently active/being treated)	1.	
	2.	
	3.	
	4.	
	5.	
	6.	
	7.	
	8.	
	9.	

	10.	
	11.	
	12.	
Specifically ever diagnosed with:		
a. Coronary Heart Disease/AMI	 Yes	 No
b. Angina	 Yes	 No
c. Diabetes	 Yes	 No
d. Stroke	 Yes	 No
e. Transient Ischaemic attack	 Yes	 No
f. Peripheral vascular disease	 Yes	 No
g. Hypertension	 Yes	 No
h. Hypercholesterolemia	 Yes	 No
i. Familial Hypercholesterolemia	 Yes	 No
j. Myopathy	 Yes	 No
Exposure to the following drugs in last		
a. Statins	 Yes	 No
b. Ezetimibe	 Yes	 No
c. Fibrates	 Yes	 No
d. Niacin	 Yes	 No
e. Anti-hypertensives	 Yes	 No
f. Anti-platelets	 Yes	 No
Pregnant?	 Yes	 No
Breast Feeding?	 Yes	 No
Smoking status	 Never Smoked	
	 Ex-smoker	
	 Current smoker	
IF ex-smoker:		
Time since quitting		
Estimated quantity/day when was smoking		
Duration of smoking history (years)		
IF current smoker		
Estimated quantity/day		
Duration of smoking history (years)		
Family history of heart disease	 Yes	 No
Age of Diagnosis in male 1 st degree relative		
Age of Diagnosis in female 1 st degree		

Current Antiretroviral Medications			
Trade Name	Generic Name	Daily Dose	Start Date
1.			
2.			
3.			
4.			
5.			
6.			
Concomitant Medications / Supplements			
Trade Name	Generic Name	Daily Dose	Start Date
1.			
2.			
3.			
4.			
5.			
6.			
7.			
8.			
9.			
10.			
11.			
12.			
13.			
14.			
15.			
16.			
Medication Allergies			
Name of Medication	Description of allergy		
1.			
2.			
3.			
4.			
5.			

Examination	
Height (m)	
Weight (kg)	
Waist circumference (cm)	
Peripheral pulses	 present  absent
Systolic Blood Pressure	
Diastolic Blood Pressure	
Physical examination (Document any relevant abnormalities)	
Date ECG performed	
Date cIMT performed	
Date cPWV performed	
Date bloods taken	
Once Results available:	
Creatinine clearance	
Framingham Risk score	
Is patient eligible for enrolment	 Yes  No
If No, please document why	
If yes, Randomisation number	

